# 10.6 Clinical Investigation Duration

Recruitment of patients:

Point of enrolment:	June 2022
Enrolment period:	June 2022-December 2023

	Clinical Investigation Code:	Date
SyntheticMR	CIP-003, Version K	2023-12-21

Expected duration of each	1 day
subject's participation:	
Total expected duration of	18 months
the clinical investigation:	

# Recruitment of healthy controls:

Enrolment period:	August 2023-December 2023
Expected duration of each	1 day
subject's participation:	

# 10.7 Clinical Investigation Procedures

The assessments and procedures that will be performed during the clinical investigation are shown in the table below.

	Clinical Investigation Code:	Date
SyntheticMR	CIP-003, Version K	2023-12-21

#### 10.7.1 Schedule of Clinical Investigation Procedures / Assessments

Table 5: Schedule of the Clinical Investigation procedures

	Image Acquisition	Image Review			
Assessment	Visit 1 MR exam	Generation of Synthetic Images	Image Review Part I 	Image Review Part II	Transfer of Image Review data
Responsible	Site	Sponsor	Reader	Reader	Sponsor
eCRF 	Viedoc	Viedoc	CARPL	CARPL	Viedoc
Subject visit	Х				
Informed consent	Х				
Subject Eligibility Verification	Х				
Demography	Χ				
MR Scanning	Х				
Use of 3D-QALAS	Х				
Anonymization of MRI	Х				
Upload of MR images in eCRF	Х				
Adverse events	Х				
Device Deficiencies	Х	Х			
Site-determined diagnosis	Х				
Subject termination	Х				
Use of Investigational Device SyMRI		х			
Image review by readers			Х	Х	
Transfer of image review data from CARPL eCRF to Viedoc eCRF					Х

<sup>1Two eCRFs will be used in this clinical investigation; Viedoc eCRF for subject-related data and CARPL eCRF for image review data. When image review is complete, image review data will be extracted from CARPL and uploaded in Viedoc for archiving purposes.

# 10.7.2 Image Acquisition

#### 10.7.2.1 Visit 1 – MR exam

Before any investigation-related procedures are initiated, the informed consent (and if applicable assent) must be signed and dated by the subject (or their legally acceptable representative and/or witness, as applicable) and by the Investigator who gave the subject the verbal and written information. The original document will be retained in the Investigator Site File (ISF) and a copy provided to the subject. For further details on the informed consent process please see section 18.

After written informed consent has been obtained and it has been confirmed that the subject fulfills all the inclusion criteria and none of the exclusion criteria, the subject will be considered enrolled in the clinical investigation. The subject will be allocated to a unique subject identification number and demographic data will be collected.

<sup>2The image review will be conducted over 2 sessions (Part I and Part II) with a 4-week memory washout period in-between to minimize recall bias. The blinded reader will evaluate the synthetic MR images of a case in one session and the conventional MR images of the same case in the other session.

	Clinical Investigation Code:	Date
SyntheticMR	CIP-003, Version K	2023-12-21

The subject will then undergo an MRI scan which will consist of:

- 1. the MRI scan that the subject was originally scheduled for, and
- 2. the additional investigational MRI scan (=1-4 additional pulse sequences depending on subject's routine protocol, corresponding to an addition of 5-20 minutes to the length of the subject's scheduled scan)

For the healthy controls, a screening form will be used to identify eligible subjects. Subjects interested in participating in the study will be interviewed over phone according to the screening form by PI or delegate. The screening form is designed to rule out subjects with important medical history that could interfere with the study's objective to include healthy controls.

Healthy controls that pass the screening will be scheduled for an MRI. On the day of the MRI the informed consent form will be signed and dated by the subject and investigator or delegate.

For the healthy controls, only the investigational scans specified in Table 6 below will be performed.

**NB:** MRI scans for the investigation should be performed before any gadolinium-based contrast agent is given to the subject.

For the pediatric population, anesthesia is allowed if needed for the scheduled MRI and should follow site's clinical routines. These subjects will be included in the sub-group with pediatric subjects receiving anesthesia (Sub-group Anesthesia). Children having anesthesia will be carefully monitored by licensed anesthesiologists throughout the whole MR procedure. Sedation and general anesthesia are sometimes utilized, most frequently in children less than 6 years, in order to minimize the motion artifacts that can accompany children.

Use of contrast agents and anesthesia will be collected in the Viedoc eCRF.

#### 10.7.2.1.1 MRI Protocol

All MRI scans will be performed on a 3.0T MRI from Philips. For the investigation, images will be acquired using a fixed set of scanning parameters according to Table 6. The resolution will be similar for all sequences or as close as possible depending on MRI scanner.

Table 6: Acquisition	parameters fo	or 3D-QALAS i	and conventional .	sequences
----------------------	---------------	---------------	--------------------	-----------

Imaging Parameters	3D T1w	3D T2w	3D T2w FLAIR	3D-QALAS
FOV (mm)	220-250	220-250	220-250	220-250
Resolution	0.9-1.2 mm iso	0.9-1.2 mm iso	0.9-1.2 mm iso	1.2 mm iso
TR				Shortest
TE				2.3
TI	Site dependent	Site dependent	Site dependent	-
ETL				150
Bandwidth (Hz/px)				393
Acceleration technique	SENSE or CS-SENSE	SENSE or CS-SENSE	SENSE or CS-SENSE	CS-SENSE
Scan time (estimate)	2-4 min	2-4 min	3-6 min	5-6 min

Since this is a multi-site study with six sites, some difference in the image acquisition between the conventional images will need to be accepted. For example, resolution is allowed to range between 0.9-1.2 mm isotropic for the conventional images. FOV can vary depending on patient head size. Acceleration technique and amount of acceleration may also be different for conventional images from the different sites.

If any of these sequences are available in the standard protocol, with the requested resolution, this will be used as input for this clinical investigation. It is likely that some of these sequences with the specified resolution will need to be added after the routine clinical scan. This means that depending on the standard protocol used by the site for the specific clinical question, this may add an extra 1-4 sequences

	Clinical Investigation Code:	Date
SyntheticMR	CIP-003, Version K	2023-12-21

for the subject. The conventional 3D images can be generated with either Turbo Spin Echo sequences or Gradient Echo sequences, therefore all imaging parameters are not specified beforehand.

After completed MRI scan, subject ends his/her participation in the clinical investigation.

## 10.7.2.1.2 Anonymization of MRI files

Before DICOM images are uploaded to the Viedoc eCRF the images need to be anonymized. For the sites that have processes and tools in place for how to correctly anonymize DICOM images this process can be used.

SyMRI requires certain DICOM tags to work properly. A DICOM Conformance Statement is available from SyntheticMR specifying the requirements. To make sure these are not removed during anonymization, a test scan matching the study protocol should be acquired, anonymized and evaluated. If required tags are removed the anonymization process will need to be adjusted.

If necessary, the Sponsor can recommend site with tools and guide for how to safely and efficiently anonymize DICOM images.

## 10.7.2.1.3 Labelling and uploading of MRI files

After anonymization, a zip file should be created, containing all DICOM images from all four investigational sequences (3D-T1w, 3D-T2w, 3D-T2w FLAIR and 3D-QALAS). The zip file should be named with site number and subject ID as in the example below. The zip file can then be uploaded in the Viedoc eCRF.

Example file name 01-101 02-003

#### 10.7.2.1.4 Site-determined diagnosis

MR images acquired during the MRI scan will be sent to a radiologist for evaluation as per site's clinical routines. The site will decide the site-determined diagnosis for each subject on the basis of the results from MR imaging studies and work-up performed according to the standard of care by clinical neuroradiologists. This means that the radiologist will have access to the subject's medical records, and that the site-determined diagnosis will be based on more information than what is available for the readers in this clinical investigation, e.g. for the site determined diagnosis the neuroradiologist may also have access to DWI or SWI which will not be available in this clinical investigation.

For the healthy control group, the site determined diagnosis will be considered normal/no finding if the PI determine that no pathology is identified in the brain on the conventional MRI. Minor non-exclusionary incidental findings will be allowed for the healthy control group in order to take into consideration normal variance that is typically seen in MR imaging and normal ageing. The following list is used to categorize incidental findings:

#### Non-exclusionary incidental findings

- 1. Non-neoplastic cysts: small (<2cm) arachnoid cyst, pineal gland cyst, enlarged perivascular spaces
- 2. Vascular encephalopathy, defined as Fazekas grade 0 or 1, in patients older than 18 years old **Exclusionary incidental findings** 
  - 3. Cysts that are larger than 2cm
  - 4. Intracranial tumors: intra-axial (tumors in brain parenchyma); extra-axial (tumors in bone and meninges)
  - 5. Vascular malformations
  - 6. Major developmental disorders
  - 7. Chronic brain injury and acquired focal or diffuse loss of normal parenchyma regardless of the etiology with the exception of age-related cerebral volume loss (e.g., prior stroke, brain

	Clinical Investigation Code:	Date
SyntheticMR	CIP-003, Version K	2023-12-21

surgery, trauma, atrophy due to neurodegenerative disease such as frontotemporal degeneration; or other causes)

8. Vascular encephalopathy, defined as Fazekas grade 2 or 3, in patients older than 18 years old

The site-determined diagnosis is considered the ground truth.

The sites report the site-determined diagnosis by using the same scale as the study readers will, see Table 7. The site should also add a summary of the radiological findings in free text with more information about type of pathology or diagnosis seen in the subject.

The site-determined diagnosis and radiological findings will be entered into the Viedoc eCRF by site personnel.

Table 7: Site-determined diagnosis is reported on the following groups

#### RADIOLOGICAL FINDING CLASSES

Infectiou	ns/Inflammatory/Demyelinating
Vascular	Disorders of the Brain
Neuro D	Degenerative Disorders and Hydrocephalus
Intracran	nial Neoplasms
Traumati	ic Lesions
Congenit	tal Malformations
Toxic and	d Metabolic conditions
N.T. 1	/N. C. P.

Normal / No findings

A subject can only belong to one pathology group. If there are more than one pathology (or pathology options) in one case, the site-determined diagnosis will be based on the most appropriate or significant pathology group.

#### 10.7.3 Image Review

When all subjects have been included and the image acquisition part of the investigation has been completed the image review can begin.

# 10.7.3.1 Generation and upload of synthetic images

Sponsor will download the MRI files from the Viedoc eCRF. By using SyMRI 15 (3D), Sponsor will post-process data from the 3D-QALAS acquisition to generate synthetic contrast weighted images with virtual scanner settings corresponding to the conventional images and thus generate synthetic 3D T1w and T2w images.

Table 8: Settings for Repetition time, Echo time and Inversion time used in SyMRI to generate synthetic images.

	T1w	T2w
TR	650	6000
TE	10	100
TI1	-	150

Sponsor will then upload the conventional and the synthetic MR images into the online imaging platform CARPL (Mahajan Imaging, India) on which the images will be evaluated by the readers. CARPL contains full DICOM viewing functionalities including windowing/level, pan, zoom, ability to show multiple series and synchronized scroll. In this investigation the readers will also use the MPR functionality (Multi Plane Reformat) to view the images in three planes. The platform also contains ability to create survey questions. A survey with questions for the investigation endpoints will be prepared by Sponsor and answered by the readers during the image review.

	Clinical Investigation Code:	Date
SyntheticMR	CIP-003, Version K	2023-12-21

## 10.7.3.2 Image Review part 1 + memory washout-period + Image Review part 2.

During the image review the readers will either read the synthetic T1w and T2w images plus a conventional FLAIR, or only read the three conventional images.

Synthetic	Conventional
Synthetic T1w	Conventional T1w
Synthetic T2w	Conventional T2w
Conventional T2w FLAIR	Conventional T2w FLAIR

The image quality will be evaluated by 5 blinded neuroradiologist by using the online imaging platform CARPL. The image review will be conducted over 2 sessions with a 4-week memory washout period in-between to minimize recall bias. Images from the same subject will be separated and read across the 2 sessions, meaning that the reader will evaluate the synthetic MR images of a case in one session and the conventional MR images of the same case in another session. To minimize bias, the reader will be blinded to the type of image being reviewed (i.e., conventional vs synthetic), and the conventional and synthetic images will be mixed in a randomized order within a reading session. All readers will evaluate all images in the investigation.

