Sedation and general anesthesia are sometimes utilized, most frequently in children less than 6 years, in order to minimize the motion artifacts that can accompany children and lead to reduced diagnostic efficacy of MRI examinations. The risks of sedation and general anesthesia themselves are very low when managed by providers with appropriate training and experience. Children having anesthesia will be carefully monitored by trained and experienced health care providers throughout the whole MR procedure. These subjects will be included in the sub-group Anesthesia.

A prerequisite for the generation of synthetic MR images with SyMRI 15 (3D) is MRI data acquired using the 3D-QALAS sequence. To date, there are no MRI scanners which are FDA-cleared for the 3D-QALAS sequence available and therefore the access to retrospective data is limited. Thus, a prospective design has been chosen for this investigation. In addition, this enables the use of a standardized MRI protocol ensuring comparable MR images from the different sites. Although the MR images are collected prospectively, the MR images acquired for the investigation will not be used for diagnostic reasons or treatment decisions which means that the subjects will not be affected by the use of SyMRI 15 (3D).

A multicenter approach has been chosen to assure timely inclusion of the pathology groups listed in section 7.1. Furthermore, the sites will consist of a mix of university hospitals and private imaging centers since it is expected that the university hospitals will handle the more unusual pathologies while the private imaging centers will handle larger volumes of the more common pathologies.

The image quality of the synthetic MR images will be evaluated by multiple readers and compared with conventional MR images. A number of 5 readers evaluating all cases in the investigation was deemed sufficient and feasible. The readers will be blinded to image type (i.e. synthetic versus conventional) and the cases will be read in a randomized order to eliminate potential sources of bias.

	Clinical Investigation Code:	Date
SyntheticMR	CIP-003, Version K	2023-12-21

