#### 12.1.2 General Statistical Methodology

Descriptive statistics of subject demographics, characteristics of readers, and performance endpoints will be summarized descriptively at the patient, reader and image level. Continuous variables will be described with mean, standard deviation, median, minimum, and maximum value, and categorical variables with numbers and percentages.

Statistical analyses will be performed on the patient level. Comparisons between conventional and synthetic MR images will be conducted using non-inferiority testing procedures.

The mean difference will be presented with corresponding two-sided 95% confidence interval. Non-inferiority will be established if the lower limit of the two-sided 95% confidence interval for the mean difference (i.e., intercept) is strictly greater than a pre-specified non-inferiority margin. The primary analyses will be performed on the full analysis set. Separate analyses on adult and pediatric sub-populations, and separate analyses by reader, will also be performed.

For the primary and secondary endpoints, a non-inferiority margin of -0.05 will be used. All tests will be one-sided and conducted at significance level  $\alpha$ =0.025. In case of a successful non-inferiority test for the two primary performance endpoints, the entire probability mass  $\alpha$ =0.025 will be transferred to the secondary performance endpoints in the order specified in Section 10.2.2 *Secondary performance endpoints*. Non-inferiority will then be declared for all secondary performance endpoints with a successful non-inferiority test until the first encounter of a non-successful non-inferiority test. Estimates and confidence intervals of remaining performance endpoints will be presented descriptively but not considered as confirmatory findings.

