#### 12.1.3 Primary Performance Analysis

Sensitivity of pathological findings

The sensitivity of pathological findings will be calculated as the sample proportion of true positive (pathological) findings across all patients and readers. The difference in sensitivity between synthetic

	Clinical Investigation Code:	Date
SyntheticMR	CIP-003, Version K	2023-12-21

and conventional MR will be evaluated using non-inferiority testing procedures with GEE for binary variables as described in Section 12.1.1 General Statistical Methodology. A non-inferiority margin of -0.05 will be used.

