#### 13.2 Data Management – Image review part

The following work will be done by the sponsor during the image review part of the investigation:

DICOM images and information about site-determined diagnosis will be downloaded from Viedoc eCRF and stored in a suitable structure. Sponsor will then generate synthetic contrast weighted images using investigational device SyMRI 15 (3D) with an automated script. Some DICOM tags (e.g. study and series description) need to be adjusted on both conventional and synthetic images in order to completely blind readers to the type of image they review. The images will be given a new identifier to be used for the Image Review part.

The contrast weighted images will then be upload to CARPL. Sponsor will assign the cases to the readers for Image Review part 1. When all readers have completed the reading, the access to the images from part 1 will be removed. Sponsor will then assign the cases to the readers for Image Review part 2. After the memory washout period the readers can start Image Review part 2.

When part 2 of the Image Review is completed, the Sponsor will download the answers from image review part 1 and part 2 from CARPL and will incorporate the answers with the original Subject ID and site-determined diagnosis. This data will be transferred to Viedoc eCRF for long-term storage and will be analyzed according to the SAP.

	Clinical Investigation Code:	Date
SyntheticMR	CIP-003, Version K	2023-12-21

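### The plan does not state how each case's image type is allocated to the first or second reading session, and the visible analysis text names no order term; balancing and adjusting would recover a little precision at almost no cost.

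*Combined protocol and SAP*

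**What the plan says.** Section 10.7.3.2 puts the two image sets of a case in different sessions: "the reader will evaluate the synthetic MR images of a case in one session and the conventional MR images of the same case in another". A washout separates them: "The image review will be conducted over 2 sessions with a 4-week memory washout period in-between to minimize recall bias". On randomisation it states that "the conventional and synthetic images will be mixed in a randomized order within a reading session", and Section 7.2 adds that "the cases will be read in a randomized order to eliminate potential sources of bias". The design is fully crossed: "All readers will evaluate all images in the investigation". The same conventional FLAIR series accompanies both reads of a case.

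Section 13.2 gives the assignment to the sponsor: "Sponsor will assign the cases to the readers for Image Review part 1", and likewise for part 2. By then the sponsor has downloaded the site-determined diagnosis. No allocation rule is given there or elsewhere in the visible text.

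For the analysis, Section 12.1.2 takes the confidence limit "for the mean difference (i.e., intercept". Section 12.1.3 refers to "non-inferiority testing procedures with GEE for binary variables as described in Section 12.1.1 General Statistical Methodology". Section 12.1.1 lists the analysis populations, and no GEE model is written out there or in Section 12.1.2. Section 10.7.8 reports that no potential confounders were identified.

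**The concern.** The reading scheme is a two-period crossover in which the unit is a case read by one reader. If accuracy changes between sessions, each within-reader difference moves up when synthetic is read second and down when conventional is read second. These shifts cancel only as far as the two orders are balanced.

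Randomising presentation order within a session does not settle which image type falls in which session. Four matters are left open: the ratio of the two orders, any balance by pathological or control status, whether the five readers share one list, and whether the list is random. The sensitivity endpoint uses only pathological cases and the specificity endpoint only controls, so balance matters within each group.

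At stake are a small loss of precision and a chance shift in each primary difference, judged against a margin of 0.05. The washout shows that the plan itself regards carry-over between sessions as possible.

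**Working it through.** **Inputs from the protocol.** Margin 0.05 (Section 12.1.7); one-sided alpha 0.025, power 90% per primary endpoint and 80% jointly (Section 12.4); 90 pathological cases, 90 controls and 5 readers (Section 12.2).

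**Assumptions not in the documents.** A true difference of zero, and an additive accuracy gain s of 3 to 5 points from session 1 to session 2.

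**1. The plan's own figures.** With independent endpoints, joint power is 0.90 × 0.90 = 0.81, in line with the stated 80%. The 180 subjects cannot be rebuilt, because the assumptions behind them are not in the text available. The standard error that gives 90% power is

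SE = 0.05 / (1.960 + 1.282) = 0.01542, so SE² = 0.000238.

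**2. Chance shift.** Each paired difference shifts by +s or −s according to order. If order is drawn by simple chance, the mean shift has expectation zero and SD s/√90 when all readers share one list, or s/√450 when each reader has a separate list (90 × 5 = 450). Power = Φ(0.05/√(SE² + SD²) − 1.96).

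| s | List | SD of shift | 95% range (share of margin) | Extra variance | Power per endpoint | Joint power |
|---|---|---|---|---|---|---|
| 0.03 | shared | 0.0032 | ±0.0062 (12%) | 4% | 88.8% | 78.8% |
| 0.05 | shared | 0.0053 | ±0.0103 (21%) | 12% | 86.6% | 75.0% |
| 0.03 | separate | 0.0014 | ±0.0028 (6%) | 1% | 89.8% | 80.6% |
| 0.05 | separate | 0.0024 | ±0.0046 (9%) | 2% | 89.3% | 79.8% |

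For example, with s = 0.05 and a shared list, 0.05/√90 = 0.0053, and 0.0053²/0.000238 is about 12%.

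**3. Simulation check.** 90 cases, 5 readers, assumed accuracy 88%, cluster-robust intervals, 4,000 runs per setting. The baseline SE here is smaller than 0.01542, so the power figures compare only with each other. At s = 0.05 and a true difference of zero:

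- shared random list, no order term: SD of the estimate 0.0152, power 0.913;
- shared random list, order term: SD 0.0142, power 0.937;
- balanced within each reader, order term: SD 0.0134, power 0.957.

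The order term removes 0.0152² − 0.0142² = 0.000029 of variance, close to s²/90 = 0.000028, so the formula in step 2 describes the part that can be recovered. With no session effect, power was about 0.97. A binary session effect also creates extra discordance, which neither balance nor the term removes.

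**4. Error rate.** At a true difference of −0.05, with no order term, the rejection rate was 0.034 to 0.044 with s = 0.05 and 0.034 to 0.041 with s = 0. Both ranges exceed 0.025, which is a feature of the simulated interval and not of the session effect. The difference between them is within simulation error, about √(0.04 × 0.96/4000) = 0.003 per rate.

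**5. Smallest stratum.** Healthy controls are all adults, and the pediatric pathology targets in Table 4 sum to 4 + 4 + 4 + 7 + 7 + 4 + 2 = 32 of 55. If those targets are met, at most 23 pediatric controls remain. With a shared list and s = 0.05, the SD of the shift in pediatric specificity is then at least 0.05/√23, about 1.0 point.

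**The case against.** Mixing both image types in every session rules out the worst case, in which one type is always read first. The safeguards make a large session effect less likely: a four-week washout, removal of access to part 1 images, blinding to image type and site diagnosis, and readers with more than ten years' experience. No feedback to readers is described. Under random allocation, an excess of synthetic-second cases is no more likely than the reverse, and an interval clustered on case already carries the extra variance. All of this stands, and it keeps the point minor.

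Three stronger readings are tempting, and the documents support none of them.

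- *The order is unbalanced.* The text is silent on the allocation, and silence does not show imbalance.
- *The result is biased, because the sponsor knows truth and image type when assigning cases.* Nothing says the assignment is non-random. If 60% of cases did share one order and s were 0.05, the shift would be 0.05 × (0.6 − 0.4) = 0.010. Power would fall to 73.7% in one direction, or one-sided error would rise to 9.5% in the other. That is a reason to document the list, not evidence of bias.
- *The model has no session term.* The full GEE is not visible and its specification may have been removed from the public text. An intercept can also remain the mean difference when a centred order term is present.

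**Conclusion.** The point holds as a gap in specification with a modest consequence. The visible text states neither how image type is allocated to session nor that the allocation is balanced by reader or truth status, and it names only an intercept for the mean difference.

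If the allocation is random, the cost is precision and a chance shift in either direction, without inflated error. Sharing one list across readers makes the cost noticeable: joint power of about 79% to 75% over the assumed range, against the stated 80%. With separate lists it is nearly negligible. These sizes rest on an assumed additive session effect of 3 to 5 points and a true difference of zero, neither of which the documents give. The conclusion of the trial is not called into question.

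**What to change.** Before any read, fix and file a random list in which half of the cases are synthetic-first. Block it by truth status, and preferably also by adult or pediatric status, and draw it separately for each reader. Reading starts only after acquisition is complete (Section 10.7.3), so the stratum sizes will be known.

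In the GEE for the paired difference, add order coded ±1/2, unless the full model already contains it. The intercept then remains the order-adjusted difference. The term also covers any imbalance left when incomplete pairs are dropped under Sections 12.10 and 12.11.

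The cost is one allocation list and one covariate. Answers are downloaded by part (Section 13.2), so session is already recorded.

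This removes an additive session effect. It does not deal with a reader who recalls a case and repeats the first answer: that makes the two reads more alike and pulls the difference toward zero under either order. The washout remains the safeguard against that.
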